8. DEFINITION OF ANALYSIS POPULATIONS

The “Safety” population will consist of all subjects who received at least one dose of study drug or placebo, and have at least one postdose safety assessment.

The “Pharmacokinetic” population will consist of all subjects who received at least one dose of study drug and have evaluable PK data. Subjects may be excluded from the PK summary statistics and statistical analysis if a subject has an adverse event of vomiting that occurs at or before 2 times median time of maximum observed drug concentration (t_{max}).

All protocol deviations that occur during the study will be considered for their severity/impact and will be taken into consideration when subjects are assigned to analysis populations.

9. STATISTICAL METHODOLOGY

9.1 General

Data listings will be provided for all data that is databased. Summary statistics and statistical analysis will only be presented for data where detailed in this SAP. For continuous data, summary statistics will include the arithmetic mean, arithmetic standard deviation (SD), median, min, max and N; for log-normal data (e.g. the PK parameters: AUCs and C_{max}) the geometric mean and geometric CV% will also be presented. For categorical data, frequency count and percentages will be presented. Data listings will be provided for all subjects up to the point of withdrawal, with any subjects excluded from the relevant population highlighted. Summary statistics and statistical analyses will generally only be performed for subjects included in the relevant analysis population. For the calculation of summary statistics and statistical analysis, unrounded data will be used.

Mean change from baseline is the mean of all individual subjects’ change from baseline values. Each individual change from baseline will be calculated by subtracting the individual subject’s baseline value from the value at the timepoint. The individual subject’s change from baseline values will be used to calculate the mean change from baseline using a SAS procedure such as Proc Univariate.

Data analysis will be performed using SAS[®] Version 9.3 or greater.

9.2 Demographics and Subject Disposition

Subject disposition will be listed. The demographic variables age, sex, race, ethnicity, country of enrolment, site ID, body weight, height and body mass index will be summarized and listed.

9.3 Pharmacokinetic Assessment

9.3.1 Pharmacokinetic Analysis

Plasma concentrations of lasmiditan (LY573144) and its metabolites M8, M7 and M18 will be used to determine the following PK parameters, when possible:

| Parameter | Units | Definition |
|----------------------------|---------|---|
| AUC(0-∞) | ng.h/mL | area under the concentration versus time curve from zero to infinity |
| AUC(0-t _{last}) | ng.h/mL | area under the concentration versus time curve from time zero to time t, where t is the last time point with a measurable concentration |
| %AUC(t _{last} -∞) | % | percentage of AUC(0-∞) extrapolated |
| C _{max} | ng/mL | maximum observed drug concentration |
| t _{max} | h | time of maximum observed drug concentration |
| t _½ | h | half-life associated with the terminal rate constant (λ_z) in non-compartmental analysis |
| CL/F | L/h | apparent total body clearance of drug calculated after extra-vascular administration (LY573144 only) |
| V _z /F | L | apparent volume of distribution during the terminal phase after extra-vascular administration (LY573144 only) |
| V _{ss} /F | L | apparent volume of distribution at steady state after extra-vascular administration (LY573144 only) |
| MR | | metabolic ratio ^a |

^a = no molar correction will be applied since the metabolites are very similar in molecular weight and within 5% of the molecular weight for lasmiditan.

Additional PK parameters may be calculated, as appropriate. The software and version used for the final analyses will be specified in the clinical study report. Any exceptions or special handling of data will be clearly documented within the final study report.

Formatting of tables, figures and abbreviations will follow the Eli Lilly Global PK/PD/TS Tool: NON-COMPARTMENTAL PHARMACOKINETIC STYLE GUIDE. The version of the tool effective at the time of PK analysis will be followed.

General PK Parameter Rules

- Actual sampling times will be used in the final analyses of individual PK parameters, except for non-bolus pre-dose sampling times which will be set to zero. For non-bolus, multiple dose profiles, the pre-dose time will be set to zero unless a time deviation falls outside of the protocol blood collection time window which is considered to impact PK parameter derivation.
- C_{max} and t_{max} will be reported from observed values. If C_{max} occurs at more than one time point, t_{max} will be assigned to the first occurrence of C_{max} .
- AUC parameters will be calculated using a combination of the linear and logarithmic trapezoidal methods (linear-log trapezoidal rule). The linear trapezoidal method will be applied up to t_{max} and then the logarithmic trapezoidal method will be used after t_{max} . The minimum requirement for the calculation of AUC will be the inclusion of at least three consecutive plasma concentrations above the lower limit of quantification (LLOQ), with at least one of these concentrations following C_{max} . $AUC_{(0-\infty)}$ values where the percentage of the total area extrapolated is more than 20% will be flagged. Any $AUC_{(0-\infty)}$ value excluded from summary statistics will be noted in the footnote of the summary table.
- Half-life ($t_{1/2}$) will be calculated, when appropriate, based on the apparent terminal log-linear portion of the concentration-time curve. The start of the terminal elimination phase for each subject will be defined by visual inspection and generally will be the first point at which there is no systematic deviation from the log-linear decline in plasma concentrations. Half-life will only be calculated when a reliable estimate for this parameter can be obtained comprising of at least 3 data points. If $t_{1/2}$ is estimated over a time window of less than 2 half-lives, the values will be flagged in the data listings. Any $t_{1/2}$ value excluded from summary statistics will be documented in the footnote of the summary table.
- A uniform weighting scheme will be used in the regression analysis of the terminal log-linear portion of the concentration-time curve.
- The parameters based on observed concentration at last quantifiable timepoint (C_{last}) will be reported.

Individual PK Parameter Rules

- Only quantifiable concentrations will be used to calculate PK parameters with the exception of special handling of certain concentrations reported below the lower limit of quantitation (BQL). Plasma concentrations reported as BQL will be set to a value of zero when all of the following conditions are met:
 - The compound is non-endogenous.
 - The samples are from the initial dose period for a subject or from a subsequent dose period following a suitable wash-out period.
 - The time points occur before the first quantifiable concentration.
- All other BQL concentrations that do not meet the above criteria will be set to missing.

- Also, where two or more consecutive concentrations are BQL towards the end of a profile, the profile will be deemed to have terminated and therefore any further quantifiable concentrations will be set to missing for the calculation of the PK parameters unless it is considered to be a true characteristic of the profile of the drug.

Individual Concentration vs. Time Profiles

- Individual concentrations will be plotted utilizing actual sampling times.
- The terminal point selections will be indicated on a semi-logarithmic plot.

Average Concentration vs. Time Profiles

- The average concentration profiles will be graphed using scheduled (nominal) sampling times.
- The average concentration profiles will be graphed using arithmetic average concentrations.
- The pre-dose average concentration for single-dose data from non-endogenous compounds will be set to zero. Otherwise, only quantifiable concentrations will be used to calculate average concentrations.
- Concentrations at a sampling time exceeding the sampling time window specified in the protocol, or $\pm 10\%$, will be excluded from the average concentration profiles.
- Concentrations excluded from the mean calculation will be documented in the final study report.
- A concentration average will be plotted for a given sampling time only if 2/3 of the individual data at the time point have quantifiable measurements that are within the sampling time window specified in the protocol or $\pm 10\%$. An average concentration estimated with less than 2/3 but more than 3 data points may be displayed on the mean concentration plot if determined to be appropriate and will be documented within the final study report.

Treatment of Outliers during Pharmacokinetic Analysis

Application of this procedure to all pharmacokinetic analyses is not a requirement. Rather, this procedure provides justification for exclusion of data when scientifically appropriate. This procedure describes the methodology for identifying an individual value as an outlier for potential exclusion, but does not require that the value be excluded from analysis. The following methodology will not be used to exclude complete profiles from analysis.

Data Within an Individual Profile

A value within an individual profile may be excluded from analysis if any of the following criteria are met:

- For pharmacokinetic profiles during multiple dosing, the concentration of the pre-dose sample exceeds all measured concentrations for that individual in the subsequent post-dose samples.

- For pharmacokinetic profiles during single dosing of non-endogenous compounds, the concentration in a pre-dose sample is quantifiable.
- For any questionable datum that does not satisfy the above criteria, the profile will be evaluated and results reported with and without the suspected datum.

Data Between Individual Profiles

1. If $n < 6$, then the dataset is too small to conduct a reliable range test. Data will be analyzed with and without the atypical value, and both sets of results will be reported.
2. If $n \geq 6$, then an objective outlier test will be used to compare the atypical value to other values included in that calculation:
 - a. Transform all values in the calculation to the logarithmic domain.
 - b. Find the most extreme value from the arithmetic mean of the log transformed values and exclude that value from the dataset.
 - c. Calculate the lower and upper bounds of the range defined by the arithmetic mean $\pm 3 \times SD$ of the remaining log-transformed values.
 - d. If the extreme value is within the range of arithmetic mean $\pm 3 \times SD$, then it is not an outlier and will be retained in the dataset.
 - e. If the extreme value is outside the range of arithmetic mean $\pm 3 \times SD$, then it is an outlier and will be excluded from analysis.

If the remaining dataset contains another atypical datum suspected to be an outlier and $n \geq 6$ following the exclusion, then repeat step 2 above. This evaluation may be repeated as many times as necessary, excluding only one suspected outlier in each iteration, until all data remaining in the dataset fall within the range of arithmetic mean $\pm 3 \times SD$ of the log-transformed values.

Reporting of Excluded Values

Individual values excluded as outliers will be documented in the final report. Approval of the final report will connote approval of the exclusion.

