7. SAMPLE SIZE JUSTIFICATION

Up to 36 subjects may be enrolled in order that 30 subjects (2 groups of 15) complete the study. For area under the curve (AUC) or maximum observed drug concentration (C_{max}), assuming inter-subject coefficient of variation (CV) of 40% and a sample size of 15 per group, the 90% confidence interval around the ratio of the geometric means (elderly group : non-elderly group) will have half-width of 24.3% on the log scale with 90% coverage probability.

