9.3.2 Pharmacokinetic Statistical Methodology

The PK parameter estimates will be evaluated to determine the impact of age on the PK of lasmiditan and its metabolites. Log-transformed C_{\max} and $AUC(0-\infty)$ will be evaluated in a linear fixed-effects model with a fixed effect of age group (elderly, young). The 90% confidence intervals (CIs) of the ratios of geometric means of the elderly group versus the young group will be presented. An example of the SAS code that will be used is as follows:

```
proc mixed data=xxx;  
class agegroup;  
model l_pk = agegroup / alpha=0.1;  
lsmeans agegroup / pdiff;  
run;
```

where l_pk is the log-transformed (base e) PK parameter.

The t_{\max} will be analyzed using a Wilcoxon rank sum test. Estimates of the median difference between elderly and young subjects based on the observed medians, 90% CIs and the p-value from the Wilcoxon test will be calculated.

Additional analysis will be performed if warranted upon review of the data.

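### The fixed 3 SD outlier limit, if run routinely, flags a genuine value in up to about 1 in 5 clean groups of 15, and the SAP contradicts itself on whether a flagged value must go

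*SAP*

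**What the plan says.** The rule is in SAP section 9.3.1, under the heading on data between individual profiles. For n of 6 or more, the values are log-transformed and step 2b says to "Find the most extreme value from the arithmetic mean of the log transformed values and exclude that value from the dataset". Step 2c then says to "Calculate the lower and upper bounds of the range defined by the arithmetic mean $\pm 3 \times SD$ of the remaining log-transformed values". Under step 2e, if the removed value lies outside that range, "then it is an outlier and will be excluded from analysis". On repetition: "This evaluation may be repeated as many times as necessary, excluding only one suspected outlier in each iteration".

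The introduction to the same procedure is permissive. "Application of this procedure to all pharmacokinetic analyses is not a requirement", and the method identifies a value as an "outlier for potential exclusion, but does not require that the value be excluded from analysis".

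The SAP calls the test objective and states no error rate for it. Between profiles, reporting both with and without the atypical value is specified only for n below 6. Within a profile, it is specified for any questionable value that meets neither listed criterion. For n of 6 or more between profiles, excluded values are only documented in the final report, whose approval counts as approval of the exclusion.

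The retained values feed section 9.3.2: "The 90% confidence intervals (CIs) of the ratios of geometric means of the elderly group versus the young group will be presented".

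**The concern.** A 3 SD limit suggests a false-alarm rate of about 0.3%, which applies to one value picked in advance and judged against a known SD. Here the value is the most extreme of n, and the SD comes from the other n − 1 values, 14 of them at the planned group size and 5 at the smallest permitted. Both features raise the chance that a genuine value falls outside the range.

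Dropping genuine extremes reduces the estimated between-subject SD, and with it the reported geometric CV and the width of the 90% interval for the elderly:young ratio. That ratio is the comparative result of the study and serves a secondary objective. The geometric CV is part of describing exposure in the elderly, which is the primary objective. The SAP plans nothing at n = 15 that would show a reader how much an exclusion changed the result.

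**Working it through.** **Inputs.** Section 7 gives "assuming inter-subject coefficient of variation (CV) of 40% and a sample size of 15 per group". Section 9.1 treats AUC and Cmax as log-normal, so the log-scale SD is sqrt(ln(1 + 0.40²)) = 0.3853. Section 9.3.2 gives the two-group model on log values and the 90% interval. Assumptions: log values are normal, there are no true outliers, and the test is run within each age group.

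**The plan's own figure.** The half-width at n = 15 per group is t(0.95; 28 df) × 0.3853 × sqrt(2/15) = 0.239. Section 7 states 24.3%. The two are close, and nothing below depends on the difference.

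**Flagging rate.** The distance of a value from the mean of the others, divided by their SD and by sqrt(1 + 1/(n − 1)), follows a t distribution with n − 2 df. The 3 SD limit is therefore a t cut-off of 3/sqrt(1 + 1/(n − 1)). Any of the n values could be the extreme one, so the chance that a clean group is flagged is about n × 2 × P(t(n − 2) > cut-off).

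At n = 15 the cut-off is 3/sqrt(1 + 1/14) = 2.898, the two-sided p is 0.01245, and 15 × 0.01245 = 0.187.

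| n | Formula | Simulation (400,000 groups) |
|---|---|---|
| 6 | 31.2% | 31.2% |
| 10 | 21.6% | 21.7% |
| 15 | 18.7% | 18.6% |
| 18 | 18.2% | 18.2% |
| 30 | 19.1% | 18.7% |

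**Two groups.** For one parameter, the chance that at least one of the two groups is flagged is 1 − (1 − 0.187)² = 0.34. Simulation gives 0.337.

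**Effect on the interval if every flagged value is dropped.** Two groups of 15 with log SD 0.3853 were simulated, with the rule repeated within each group and then a pooled-variance 90% t interval.

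| | All data kept | Fixed 3 SD, all flags dropped |
|---|---|---|
| Coverage, all studies | about 90% | 86.6% |
| Mean half-width, log scale | 0.237 | 0.228 |

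The width ratio is 0.228/0.237 = 0.96, so intervals are about 4% narrower on average. In the roughly one third of studies with an exclusion, coverage is about 80% and the interval about 12% narrower.

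**With an n-specific limit.** Setting n × 2 × P(t(n − 2) > c) = alpha and solving for the multiplier gives k(n) = t(1 − alpha/(2n); n − 2 df) × sqrt(1 + 1/(n − 1)). For alpha = 5% and n = 15, k = 3.584 × 1.035 = 3.71. At n = 18 it is 3.63. In simulation at n = 15 this flags 5.0% of clean groups, and coverage with every flag acted on is about 89%.

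**The case against.** The strongest reply is that 18.7% is a rate of flagging and not of loss. A reader might infer that about 1 in 5 clean groups will lose a genuine value. The SAP does not support that. Section 9.3.1 makes both the procedure and the exclusion optional, its starting point is a value already seen as atypical, and it bars using the method to remove complete profiles. The loss and coverage figures need every group to be tested and every flag to be acted on. The SAP also does not say outright that the test is run per age group on AUC and Cmax. This stands, and it makes the figures ceilings.

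It is also fair that the overall effect is modest, at about 3.4 points of coverage and 4% of width. A reader might take the 80% coverage and 12% narrowing as the general effect, but they apply only to studies with an exclusion. Under log-normality exclusions are symmetric, so the ratio itself is not biased, and the SAP attaches no equivalence bound to the interval.

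Optionality does not remove the defect. The procedure is offered as justification for excluding data, and a test that clean data fail this often justifies little. Waiting for suspicion gives limited protection, because the value tested is always the most extreme one. Step 2e, read alone, requires exclusion. At the planned group size no with-and-without comparison is specified.

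**Conclusion.** The point holds in a limited form. Under routine use on clean log-normal data, the fixed 3 SD limit flags, and permits exclusion of, a genuine value in up to about 1 in 5 groups of 15. If all flags were acted on in both age groups, about 34% of comparisons would lose a value per parameter, and the nominal 90% interval would cover about 87% with a mean width about 4% smaller. How far practice falls below these ceilings depends on judgement exercised after the data are seen, which the SAP does not constrain.

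Two textual faults stand whatever the multiplier: the conflict between the permissive introduction and step 2e, and the absence of with-and-without reporting for n of 6 or more.

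The results rest on normal log values, no true outliers, 15 per group, and the test being run within each age group. The 40% CV sets the absolute half-widths but not the flagging rates or coverage.

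**What to change.** 1. In steps 2c to 2e, replace the fixed 3 by k(n) = t(1 − alpha/(2n); n − 2 df) × sqrt(1 + 1/(n − 1)) and state alpha. With alpha = 5%, k is 3.71 at n = 15 and 3.63 at n = 18. The choice of alpha is the sponsor's; 1% would give 4.60 at n = 15.
2. Reconcile the introduction to the outlier procedure with step 2e, so that the section says one thing about whether a flagged value is excluded.
3. Extend to n of 6 or more the with-and-without reporting now specified for n below 6. Make the all-data result the main analysis unless a documented assay or dosing error explains the value.

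The cost is a few sentences in the SAP, one line of code and an extra table where a value is flagged. The downside is that an erroneous value between 3 SD and the new limit stays in the main analysis, where it can widen the interval and shift the geometric mean. At the SAP's CV, a single value 3.71 SD out moves the log mean of 15 subjects by about 3.71 × 0.3853/15 = 0.095, which is not trivial against the stated half-width of 24.3%. The with-and-without report would show this to the reader.

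### The between-profile outlier rule contradicts its own preamble on exclusion, does not name the data it tests, and at 15 per group requires no result that keeps the flagged value

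*SAP*

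**What the plan says.** All of this is in SAP section 9.3.1.

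- **Preamble (Treatment of Outliers during Pharmacokinetic Analysis).** The procedure need not be applied to every PK analysis. It "provides justification for exclusion of data when scientifically appropriate". It identifies a candidate for possible exclusion but "does not require that the value be excluded from analysis".
- **Data Between Individual Profiles, n below 6.** "Data will be analyzed with and without the atypical value, and both sets of results will be reported".
- **Data Between Individual Profiles, n of 6 or more.** A range test is used to "compare the atypical value to other values included in that calculation". Values are log-transformed, the one furthest from the mean is set aside, and mean ± 3 SD is computed from the rest. If the value falls outside that range, "then it is an outlier and will be excluded from analysis". The step may be repeated while at least 6 values remain.
- **Data Within an Individual Profile.** A questionable datum that meets no listed criterion is handled by reporting results with and without it.
- **Reporting of Excluded Values.** Excluded values are documented in the final report, and "Approval of the final report will connote approval of the exclusion".

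Section 7 plans 15 completers per group and assumes an inter-subject CV of 40%. Section 9.3.2 compares log Cmax and log AUC(0-∞) between age groups and presents a 90% confidence interval for the elderly to young ratio.

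**The concern.** Three things are badly fixed.

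1. **Conflicting instruction.** The preamble leaves the fate of a flagged value open, and step 2e closes it. Two analysts could both follow the SAP and arrive at different datasets. No criterion is given for when exclusion is scientifically appropriate.
2. **Test set not named.** The SAP does not say what makes a value atypical, whether PK parameters or concentrations are tested, or whether the two age groups are tested separately or together. Step 2b does fix which value is the candidate once a dataset has been chosen.
3. **Reporting gap where it matters.** With 15 per group the planned comparison falls on the branch with n of 6 or more. That is the one between-profile branch with no requirement to show the result that includes the value.

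If valid AUC or Cmax values are removed, the elderly geometric CV% (section 9.1, serving the primary objective in 4.1) is understated, and the interval for the age ratio (secondary objective in 4.2) is too narrow.

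**Working it through.** **Inputs.** CV 40% and 15 per group (section 7); the test steps (section 9.3.1); a two-group model on the log scale with a 90% interval (section 9.3.2). Assumptions: log-normal data without errors, one parameter, and the test run on log AUC or Cmax.

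**The plan's own figure.** The outlier rule has no figure of its own, so the design figure in section 7 serves to check the inputs.
- Log SD = √ln(1 + 0.40²) = 0.385.
- Expected half-width = t(0.95; 28) × SD × √(2/15) = 1.701 × 0.385 × 0.365 = 0.239.
- Half-width not exceeded with 90% probability = 0.239 × √(χ²(0.90; 28)/28) = 0.239 × 1.164 = 0.278.
- 1 − exp(−0.278) = 24.3%. The stated figure is reproduced as the lower-side percentage after back-transformation.

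**How often the test flags clean data.** The candidate is left out of the mean and SD it is judged against, so its standardised distance follows a t distribution with n − 2 degrees of freedom after scaling by √(1 + 1/(n − 1)). First-step rate ≈ 2n × P(t(n−2) > 3/√(1 + 1/(n − 1))).
- n = 15: 3/√(1 + 1/14) = 2.898; P(t(13) > 2.898) = 0.00622; 30 × 0.00622 = **0.187**.
- n = 6: 0.312. n = 18: 0.182. n = 30: 0.191.
- Either of two groups of 15: 1 − (1 − 0.187)² = 0.339.

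**Effect if run routinely by age group.** Simulation of 40,000 trials at each true ratio of 1, 1.3 and 1.5, with repetition as the SAP allows:

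| Quantity | All values kept | Rule applied |
|---|---|---|
| Elderly group loses a value | – | 18.5–18.9% |
| Either group loses a value | – | 34% |
| Coverage of the 90% interval | 90% | 87% |
| Coverage in trials with an exclusion | about 90% | 80–81% |
| Mean half-width, relative | 1 | 0.96 (0.88 with an exclusion) |
| Mean elderly geometric CV%, all groups | 39.5% | 37.2% |
| Mean elderly geometric CV%, flagged groups | 39.5% | 27.6% |

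The mean log ratio does not move (shift −0.0002 or smaller in size).

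**Effect if run routinely on the 30 pooled values.** At assumed true ratios of 1, 1.3 and 1.5 (the SAP states no expected age effect), 19%, 18% and 16% of trials lose a value. Coverage is 90.0%, 88.5% and 87.6%, and the mean log ratio shifts by 0.000, −0.011 and −0.013, about 1% toward 1. So the unnamed grouping changes both the rate of loss and whether there is a bias.

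**Effect under discretionary use.** The SAP gives no trigger. With an assumed one (test only groups with a value outside the 1.5 × IQR box-plot fences on the log scale), 28–29% of comparisons lose a value and coverage is 87.0–87.2%. A stricter trigger loses less, down to nothing if the test is never used.

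**When a value really is wrong.** One elderly value divided by 5, true ratio 1: the test flags it in 85% of trials.

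| Quantity | All values kept | Rule applied |
|---|---|---|
| Bias of the log ratio | −0.108 | −0.012 |
| Coverage | 90.4% | 86.3% |
| Elderly geometric CV% (truth 40%) | about 61% | about 38% |
| Root-mean-square error, log ratio | 0.178 | 0.157 |

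The all-values interval is about 27% wider (1/0.79). On clean data the corresponding root-mean-square errors are 0.141 and 0.148.

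**The case against.** **The preamble governs the section.** Step 2e can be read as the outcome once an analyst has chosen to use the test. This softens the conflict but does not remove it: the preamble denies that an identified value must be excluded, as well as that the procedure must be applied.

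**Use is optional.** A reader might infer from the simulation that a third of this trial's comparisons will lose valid data. The SAP does not support that, because step 2 starts from a value already thought atypical and the procedure is not mandatory. The routine-use figures are an upper scenario. This stands.

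**Exclusions are not hidden.** Each is documented in the final report, section 9.1 promises listings of all databased data, and section 9.3.2 allows further analysis if warranted. A reader could recompute the result. This stands, but it does not replace a required all-values result.

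**Other exclusion sentences.** It is tempting to cite the AUC sentence ("value excluded from summary statistics will be noted in the footnote of the summary table") and the concentration sentence ("Concentrations excluded from the mean calculation will be documented in the final study report") as proof that the unit tested is ambiguous. They follow the flag for extrapolated area and the sampling-window rule respectively, so they do not concern the range test. The ambiguity rests on the test's own generic wording.

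**Approval.** A reader might infer that approval of the report is the only approval of an exclusion. The SAP says only that it implies approval.

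**The rule has merit.** In the five-fold error case it gives less bias and smaller error than keeping all values. This stands, and it is a reason not to impose an all-values default.

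**Conclusion.** The point holds as a defect of wording, definition and reporting. The contradiction and the missing with-and-without result at n of 6 or more can be read directly from the text. The flag rate of about 19% in clean groups of 15 follows from the rule's arithmetic under log-normality.

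The consequence for the trial is conditional. If the test is run on log AUC or Cmax by age group, the effect lies between nil (never used) and the routine-use case: about 34% of comparisons losing a valid value, coverage of about 87% overall and about 80% where a value is removed, and mean elderly geometric CV% of 37.2% instead of 39.5%. The fall to about 28% applies only to groups with an exclusion.

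A reader might infer that the study's conclusion could be reversed. Section 9.3.2 attaches no decision limit to the ratio, and testing by group produces no directional shift. The harm is overstated precision. The change should be made, but the case for it should not rest on the routine-use figures.

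**What to change.** 1. Reword step 2e to agree with the preamble, for example: *it is identified as an outlier and may be excluded when scientifically appropriate, with the reason documented*.
2. State that the between-profile test is applied to log-transformed PK parameters within age group.
3. For every n, report the geometric mean, geometric CV%, elderly to young ratio and 90% interval both with all values and without any excluded value.

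The sponsor should also fix in advance which of the two results is the main one. Making all values the default is an option and not part of the required change, because an erroneous value with no documented cause would then stay in the main result, at the cost shown in the five-fold example.

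The cost is SAP wording and one extra model run per flagged parameter. Sample size and data collection are unaffected, and the population exclusions in section 8 and the within-profile rules can stay as they are.
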